#### AEs include the following:

1. An exacerbation, or an unexpected increase in frequency or intensity of a pre-existing condition (other than condition under investigation), including intermittent or episodic conditions.
2. Significant or unexpected worsening or exacerbation of the condition/indication under investigation.
3. A suspected drug interaction.
4. An intercurrent illness.
5. Any clinically significant laboratory abnormality.

#### An AE does not include:

1. Anticipated day-to-day fluctuations of any pre-existing conditions, including the disease under study.
2. Signs and symptoms of the disease under study that do not represent a significant worsening or exacerbation.
3. Expected progression of the disease under investigation.
4. Abnormal laboratory findings that are grade 1 or 2 and are considered clinically insignificant.

Serious adverse events (SAE) are any events occurring that result in any of the following outcomes:

1. Subject death
2. Life-threatening adverse event
3. Inpatient hospitalization or prolongation of existing hospitalization
4. Persistent or significant disability/incapacity
5. Congenital anomaly or birth defect

A life-threatening event is defined as any adverse event that places the subject, in the view of the investigator, at immediate risk of death from the reaction.

Note: In addition to the above criteria, adverse events meeting any of the below criteria, although not serious per ICH definition, are reportable to the BMS in the same timeframe as SAEs to meet

certain local requirements. Therefore, these events are considered serious by BMS for collection purposes.

- Is another important medical event
- Is a new cancer (that is not a condition of the study)
- Is associated with an overdose.

#### Severity rating/grading scale

Adverse events are classified by organ system and graded by severity according to the current NIH Common Terminology Criteria V. 5, as described in Appendix A. The defined grades use the following general guidelines:

0	No adverse event or within normal limits
1	Mild adverse event
2	Moderate adverse event
3	Severe adverse event
4	Life-threatening or disabling adverse event
5	Fatal adverse event

All adverse events will be recorded from time of treatment initiation through 30 days after the final dose of study treatment, as well as any time after these 30 days for events that are believed to be at least possibly related to study treatment. Please note: SAEs, regardless of relationship, occurring from the time of consent  100 days after the final dose of nivolumab will be collected and reported as per section E.1.

Appropriate clinical, diagnostic, and laboratory measures to attempt to delineate the cause of the adverse reaction in question must be performed and the results reported. All tests that reveal an abnormality considered to be drug- or vaccine-related will be repeated at appropriate intervals until the course is determined or a return to normal (or pre-treatment) values occurs. Information will be recorded as noted above.

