g If not performed within 7 days of this visit

h 28 days +/- 7d after off-study date, if prior to week 48, otherwise this visit not required

i If not already collected within previous 60 days

j Only use GM-CSF adjuvant if serum PSA at week 4 (V3) is higher than that obtained at day 1 (V1).

k Can be +/- 14 days of this visit

l PSA values used for screening/eligibility should all be from same clinical laboratory; for day 1 and subsequent visits, all PSA values should be from same lab, but not necessarily from same lab as used for screening

m Physical exam to include vital signs and ECOG status

n Physical exam does not need to be repeated on Day 1 if obtained within 14 days prior to the visit

o PSA obtained at week 4 and used to determine whether GMCSF will be added can be obtained within 7 days of the visit

p Patients will be followed for adverse events for 90 days after the last dose of nivolumab

q NaF PET/CT within +/- 7 days of study visit, exceptions may be allowed with prior approval from the study PI. The same PET/CT scanner should be used for each individual subject.

r NaF PET/CT should NOT be done within 2 days of GM-CSF injection.

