## **7. Definition and Management of Limiting Toxicities and Adverse Events**

A treatment-limiting toxicity will be defined as any Grade 3 or greater toxicity (using the NCI Common Terminology Criteria version 4), or a specific Grade 2 event as described below that affects agent dosing, with an attribution of at least possibly related to the study or treatment procedures, and occurring between the pre-study visit and within one month of the final study vaccine treatment or within 90 days of the last treatment with nivolumab (whichever is later). If a patient develops Grade 3 toxicity with an attribution of at least possibly related to nivolumab and unlikely related (or unrelated) to pTVG-HP, the nivolumab treatment will be held until the toxicity resolves to Grade 1 or less, with the vaccine schedule continuing as per protocol. In general, if a patient develops a second Grade 3 event (or any Grade 4 event) believed to be at least possibly

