R. Week 84 visit (84 +/- 14 days after week 72 visit)

1. Physical examination, including vital signs, symptoms assessment, and ECOG performance score
2. Blood draw CBC, chemistry panel, PSA and PAP.

S. Week 96 visit (84 +/- 14 days after week 72 visit) – END OF STUDY

1. Physical examination, including vital signs, symptoms assessment, and ECOG performance score
2. Blood draw CBC, chemistry panel, PSA and PAP.
3. CT scan of abdomen and pelvis, and bone scan (can be performed +/- 7 days of this visit)

T. 28-Day Follow Up Visit (28 +/- 7 days after Off-study date, if prior to week 48)

Patients will come off study at the time of disease progression, undue toxicity, or at the discretion of the patient and/or treating physician that it is not in the interest of the patient to continue treatment. A separate follow-up visit is not required for patients completing the week 48 evaluation, however for patients coming off study prior to week 48, 28-day follow up visit will include the following:

1. Physical examination, symptoms assessment, and ECOG performance score.
2. Blood draw for CBC, chemistry panel, serum PSA and PAP
3. IF NOT ALREADY COLLECTED WITHIN PREVIOUS 60 DAYS: 10 ml peripheral blood (red-top tubes) for sera to evaluate antibody responses, and 100 ml peripheral blood (green-top heparinized tubes) for T-cell response evaluation

U. Long-term Follow-Up

Subjects will be contacted by telephone (if not already being seen in clinic) annually for 2 years following the last DNA vaccination to collect clinical information to identify any potential long-term risks. This information has been requested by FDA for all gene delivery trials to assess potential long-term risks. The specific information to be collected annually will include:

- Date of contact
- Current medications
- Hospitalizations (dates and reasons for hospital admission)

- Stage of prostate cancer, treatments for prostate cancer, and recent serum PSA level
- New cancer diagnoses
- New autoimmune disorders
- New hematologic or neurologic disorders
- Other new medical diagnoses
- Date of death if patient deceased

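### Adverse events of any attribution are recorded to 30 days in Section 12.A but followed to 90 days after nivolumab in the study calendar, and patients who leave before week 48 have no scheduled toxicity assessment between the 28-day visit and the annual call

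*Combined protocol and SAP*

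**What the plan says.** The protocol gives several windows for adverse events after treatment.

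- **Section 12.A, severity rating/grading scale.** "All adverse events will be recorded from time of treatment initiation through 30 days after the final dose of study treatment". The sentence continues: "as well as any time after these 30 days for events that are believed to be at least possibly related to study treatment". The next sentence sets a separate rule for SAEs, regardless of relationship: those up to "100 days after the final dose of nivolumab will be collected and reported as per section E.1".
- **Study calendar, footnote p.** "Patients will be followed for adverse events for 90 days after the last dose of nivolumab". No attribution limit is given. In the calendar header the footnote is attached to the 28-day follow-up column.
- **Section 7.** A treatment-limiting toxicity can occur up to one month after the last vaccination or 90 days after the last nivolumab dose, whichever is later, but must be an event "with an attribution of at least possibly related to the study or treatment procedures".

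The follow-up schedule for patients who leave before week 48 is in calendar footnote h and Section 8.T: one visit, 28 +/- 7 days after the off-study date. Section 8.U then provides a telephone contact once a year for 2 years after the last vaccination. Patients who complete treatment have the week 48 and week 60 visits (Sections 8.O and 8.P).

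**The concern.** Safety and tolerability form a primary endpoint, and Section 10.D(2) reports toxicity rates by grade with confidence intervals, without stating an attribution restriction. Which events enter those rates should not depend on which section a site reads. A non-serious event on day 60 judged unlikely related is inside the calendar's follow-up and outside Section 12.A's recording.

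The second issue is ascertainment. Section 7 warns that immune-related events may appear several months after nivolumab stops. A rule that such events must be recorded helps only if someone learns of them. Patients who complete treatment are seen at visits through week 96, whereas early leavers are not, so detection could differ with how long a patient stayed on study. With 21 patients in the first stage and 41 in total, one missed patient moves a toxicity rate by 1/21 = 4.8 percentage points or 1/41 = 2.4 percentage points.

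**Working it through.** The plan states no figure to reproduce here. The check sets the windows side by side and then counts days.

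**Step 1: which events fall between the texts.** By schedule, vaccine and nivolumab are given at the same visits, so assume that their last doses coincide. For days 31-90 after that dose:

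- SAE, any attribution: recorded under Section 12.A (100-day rule).
- Non-serious, at least possibly related: recorded under Section 12.A (no time limit).
- Non-serious, unlikely related or unrelated: not recorded under Section 12.A, but within follow-up under footnote p.

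Only the third class is treated differently. Section 7 adds no conflict, because its 90-day definition covers only events at least possibly related, all of which Section 12.A records.

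**Step 2: patients who complete treatment.** Section 6 gives nine four-weekly doses from week 12, so the last is at week 12 + 8 x 4 = week 44. The week 48 visit is 28 +/- 3 days later, on days 25-31. The week 60 visit is 84 +/- 14 days after that, between 25 + 70 = day 95 and 31 + 98 = day 129 (nominally 28 + 84 = day 112). A visit with examination and laboratory tests therefore falls after day 90.

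**Step 3: patients off study before week 48.** Let L be the number of days from the last nivolumab dose to the off-study date. The single visit falls between days L + 21 and L + 35. The days left to day 90 run from 90 - (L + 35) to 90 - (L + 21), floored at 0. The documents do not give L, so the values below are assumptions.

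- L = 0: visit on days 21-35; 90 - 35 = 55 to 90 - 21 = 69 days uncovered.
- L = 28: visit on days 49-63; 90 - 63 = 27 to 90 - 49 = 41 days uncovered.
- L = 56: visit on days 77-91; 0 to 90 - 77 = 13 days uncovered.

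Against the 100-day SAE window the corresponding gaps are 65-79, 37-51 and 9-23 days.

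**Step 4: what the next contact collects.** The annual call in Section 8.U asks about hospitalizations, new autoimmune, hematologic or neurologic disorders and other new diagnoses. It does not ask for grade or attribution, and it asks for dates only of the contact itself, hospital admissions and death. Immune blood draws may continue after a patient leaves (Section 6.B), but they are not specified as toxicity assessments.

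**The case against.** The strongest reply is that the rules already capture the events that matter. Several stronger readings are tempting, and the documents do not support them.

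- *Late immune toxicity is excluded from recording after day 30.* It is not. Related events have no time limit and SAEs of any cause run to 100 days.
- *Section 7 contradicts Section 12.A.* It does not, because it is restricted to events at least possibly related. The mismatch is with footnote p alone.
- *Early leavers have no contact after about day 28.* The annual calls run for 2 years, Section 6 follows all subjects for delayed adverse events for 2 years after their last treatment, and immune blood draws can continue after a patient leaves.
- *Between 61% and 77% of the 90 days is uncovered.* These are 55/90 and 69/90. They hold only if the off-study date is the date of the last nivolumab dose. The visit is counted from the off-study date, so a longer lag shrinks the gap.
- *Toxicity rates would be undercounted.* The documents give neither the number of early leavers nor the rate of late events, so "could" is the most that can be said.

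It is also fair that footnote p sits on the very visit made by early leavers, so the 90-day obligation does reach them. And Section 7 keeps some patients under observation after toxicity: if only nivolumab stops, vaccine visits continue; if vaccine-related toxicity stops all treatment, the patient remains on study.

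All of this limits the point without removing it. Footnote p states an obligation but names no contact or date by which it is met, and the any-time rule for related events has the same gap.

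**Conclusion.** The point holds in a limited form. The any-attribution recording window in Section 12.A (30 days) does not match the follow-up in footnote p (90 days); the events affected are non-serious ones judged unlikely related or unrelated in days 31-90. Separately, patients off study before week 48 have no scheduled toxicity assessment between the visit at 28 +/- 7 days and the annual call. Late non-serious immune events in these patients could be missed, or learned of too late to be dated and graded well.

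The gap within the 90 days is 55-69, 27-41 or 0-13 days for assumed lags of 0, 28 and 56 days from last nivolumab dose to off-study date. Completers are not affected by the visit gap. The effect on the reported rates cannot be sized from the documents. This is an inexpensive improvement to the ascertainment of a primary endpoint and does not show that the safety analysis is invalid.

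**What to change.** 1. In Section 12.A, align the recording window for adverse events of any attribution with the 90 days after the last nivolumab dose in footnote p. Keep the any-time rule for related events and the 100-day rule for SAEs.
2. In Section 8.T and the calendar, add one telephone adverse-event check at about day 90-100 after the last nivolumab dose for patients off study before week 48, recording onset date, grade and attribution.
3. Reconcile Sections 6.B and 8.T, under which patients come off study for undue toxicity, with Section 7, under which a patient whose treatment is stopped for vaccine-related toxicity remains on study. These texts decide which patients have only the single follow-up visit.

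The cost is a wording change, one call per early leaver and slightly more data entry. The sample size and the efficacy analysis are unaffected.

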#### **B. Disease Oriented Team Meetings**

UWCCC site: This study undergoes review of subject safety at regularly scheduled Disease Oriented Team (DOT) meetings where the following are discussed as applicable: number of subjects enrolled, subject treatments given, dose holds/modifications, significant toxicities, response to treatment, and the subjects' overall status. These discussions are documented in the DOT meeting minutes.

#### **C. UWCCC Data and Safety Monitoring Committee (DSMC) Study Progress Review and Oversight**

The review of Protocol Summary Reports (PSRs) enables the UWCCC DSMC to assess whether the study should continue, continue with modifications, be suspended, or be closed. Following their review, the UWCCC DSMC will notify the sponsor-investigator of their recommendation and the authority for continuing, modifying, suspending, or closing the protocol is the responsibility of the applicable sponsor-investigator, Principal Investigator, IRB, FDA or other regulatory authority associated with the protocol.

Based on the risk level of this study, as determined by the UWCCC Protocol Review and Monitoring Committee, PSRs must be submitted to the UWCCC DSMC by the UWCCC site on a quarterly basis.

The UWCCC site is responsible for ensuring participating sites enter data used to populate the PSRs in a timely manner into the UWCCC instance of OnCore. This data includes: accrual information, Serious Adverse Events (SAEs), response to treatment, events reportable to IRB (e.g., non-compliance, unanticipated problems).

**a. UWCCC DSMC Review of Auditing and/or Monitoring Reports**

Reports created through the auditing and/or monitoring activities at all sites are submitted in real-time by the UWCCC site to the UWCCC DSMC. Summary data and/or query reports are submitted in lieu of detailed reports. Following the review of these reports, the committee may issue a request for corrective and/or preventive action(s), protocol suspension, or for-cause audit(s).

**b. UWCCC DSMC Review of Non-compliance, Unanticipated Problems, and Other IRB Reportable Events**

UWCCC site: Reports of non-compliance, unanticipated problems, and other IRB reportable events are submitted to the IRB of record for the study and to the UWCCC DSMC, via an email to [[contact]](mailto:[contact]), simultaneously.

Non-UWCCC participating site(s): Reports of non-compliance, unanticipated problems, and other IRB reportable events are submitted to the IRB of record for the site at which the event occurred and to the UWCCC site, via an email to [[contact]](mailto:[contact]), simultaneously. The UWCCC site forwards the event information to the UWCCC DSMC within 1 business day of receipt.

**c. Real-time UWCCC DSMC Review of Serious Adverse Events (SAEs)**

The UWCCC DSMC Chair, or designee, reviews all SAEs occurring on the study, regardless of site, to determine if immediate action is required.

**UWCCC site: The Principal Investigator (PI), or designee, notifies the following individuals/entities of SAEs as applicable:**

- Other investigators involved with the study at the UWCCC
- IRB of record for the study conducted at the UWCCC, per the IRB's reporting requirements
- UWCCC DSMC (Refer to section D)
- Sponsor-Investigator
- UW Institutional Biosafety Officer [[name]: [[contact]](mailto:[contact]) ]

Non-UWCCC participating sites: The site PI, or designee, notifies the following individuals/entities of SAEs as applicable:

- Other investigators involved with the study at the site
- IRB of record for the study conducted at the site, per the IRB's reporting requirements
- Institutional Biosafety Committee of record for the participating site
- UWCCC site via an email to [[contact]](mailto:[contact])

UWCCC site (Sponsor-Investigator or designee): responsibilities are noted in section E

#### **D. Serious Adverse Event Reporting**

##### **Serious Adverse Events Requiring 24-Hour Reporting**

UWCCC site: All Serious Adverse Events must be reported within 24 hours to the UWCCC DSMC Chair via an email to [[contact]](mailto:[contact]) within one business day. The OnCore SAE Details Report must be submitted along with other report materials as appropriate (FDA Medwatch Form #3500, UWCCC routing form, UWCCC Sponsor-Investigator Determination Form for FDA Reporting of Safety Events, de-identified supporting documentation available at that time of initial reporting). The UWCCC DSMC Chair reviews the information and determines if immediate action is required. Within 5 calendar days, all available subsequent SAE documentation is submitted electronically, along with a 24 hour follow-up SAE Details Report, to [[contact]](mailto:[contact]). This information is entered and tracked in the UWCCC secure, password protected computer network. Refer to the current UWCCC SAE Standard Operating Procedure (SOP) and related documents to facilitate reporting.

UWCCC site (Sponsor-Investigator): Refer to section E for sponsor-investigator responsibilities.

Non-UWCCC participating site(s): All Serious Adverse Events must be reported within 24 hours to the UWCCC site via an email to [[contact]](mailto:[contact]) and a phone call [contact]) within one business day of the site being aware of the event. The OnCore SAE Details Report must be submitted along with other report materials as appropriate (FDA Medwatch Form #3500 and de-identified supporting documentation available at that time of initial reporting). The UWCCC site sends this information, along with the completed UWCCC Sponsor-Investigator Determination Form for FDA Reporting of Safety Events, to the UWCCC DSMC Chair via an email to [[contact]](mailto:[contact]) within one business day of receipt. The DSMC Chair reviews the information and determines if immediate action is required. If immediate action is required, it is communicated by the UWCCC DSMC Chair to the UWCCC site, who is then responsible for contacting the non-UWCCC participating site. Within 5 calendar days, all available subsequent SAE documentation is submitted electronically, along with a 24 hour follow-up SAE Details Report, to the UWCCC site via an email to [[contact]](mailto:[contact]). The UWCCC site sends this information to the UWCCC DSMC Chair via an email to [[contact]](mailto:[contact]) within one business day of receipt. This information is entered and tracked in the UWCCC secure, password protected computer network.

#### **E. Sponsor-Investigator Responsibilities for SAE Review**

The sponsor-investigator (i.e., IND holder), assumes the responsibilities of the study sponsor in accordance with FDA 21 CFR 312.32. In this capacity, the sponsor-investigator reviews all reports of serious adverse events occurring on the study at the UWCCC and non-UWCCC participating sites and makes a documented determination of 1) suspectedness (i.e., whether there is a reasonable possibility that the drug caused the AE); and 2) unexpectedness (the event is not listed in the Investigator's Brochure or is not listed at the specificity or severity that has been observed) in the context of this study. SAE with suspected causality to study drug and deemed unexpected are reported as IND Safety Reports by the sponsor-investigator, or designee, to the following within 15 calendar days unless otherwise designated below:

- FDA
- All participating investigators on the study, and the external global sponsor (if applicable).
- Other oversight committees (NIH OSP)
- Study supporters within 1 day (For additional details, see section E.1):
 

**Bristol Myers Squibb (BMS)**

SAE Email Address: [contact]  
 SAE [contact]

**All fatal or life-threatening SAE** that are unexpected and have suspected causality to the study drug will be reported by the sponsor-investigator, or designee, to the following within 7 calendar days unless otherwise designated below:

- FDA
- All participating investigators on the study, and the external global sponsor (if applicable)
- Other oversight committees (NIH OSP)
- Study supporters within 1 day (For additional details, see section E.1):
 

